6.2 NIVOLUMAB

(BMS-936558, MDX1106, ONO-4538, anti-PD-1, Opdivo®) NSC# 748726,
IND# [REDACTED] (03/09/2021)

Source and Pharmacology:

Nivolumab is a fully human immunoglobulin G4 (IgG4) monoclonal antibody that selectively inhibits programmed cell death-1 (PD-1) activity by binding to the PD-1 receptor to block the ligands PD-L1 and PD-L2 from binding. The negative PD-1 receptor signaling that regulates T-cell activation and proliferation is therefore disrupted. This releases PD-1 pathway-mediated inhibition of the immune response, including the antitumor immune response. The clinical activity of nivolumab was initially evaluated in malignant melanoma and squamous non-small cell lung cancer (NSCLC), and the remarkable response rates, prolonged survival, and better safety profile were the basis of regulatory approval. Nivolumab is FDA-approved for a variety of solid tumors including advanced renal cell carcinoma (RCC).

The pharmacokinetics of single-agent nivolumab was studied in patients over a dose range of 0.1 to 20 mg/kg administered as a single dose or as multiple doses every 2 or 3 weeks. Nivolumab clearance decreases over time, resulting in a geometric mean steady state clearance (CLss) of 8.2 mL/h; the decrease in CLss is not considered clinically relevant. The geometric mean volume of distribution at steady state (Vss) is 6.8 L, and geometric mean elimination half-life is 25 days. Steady-state concentrations of nivolumab were reached by approximately 12 weeks when administered at 3 mg/kg every 2 weeks, and systemic accumulation was approximately 3.7-fold. The exposure to nivolumab increased dose proportionally over the dose range of 0.1 to 10 mg/kg administered every 2 weeks.

No formal pharmacokinetic drug-drug interaction studies have been conducted with nivolumab. The indirect drug-drug interaction potential of nivolumab was assessed using systemic cytokine modulation data for cytokines known to modulate CYP enzymes. There were no meaningful changes in cytokines known to have indirect effects on CYP enzymes across all dose levels of nivolumab. This lack of cytokine modulation suggests that

nivolumab has no or low potential for modulating CYP enzymes, thereby indicating a low risk of therapeutic protein-drug interaction.

Patient Care Implications

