ORR: A logistic regression model for overall response, stratified by the stratification factors used at randomization (age and prior therapy) will be fit, including treatment arm as a key covariate. From this model, the odds ratio for treatment arm will be reported with a 70% confidence interval. The ORR observed within each treatment arm will also be reported.

OS: A stratified, one-sided log-rank test (using the stratification factors at randomization, age and prior therapy) will be performed to compare treatment arms with alpha = 0.15. Cox proportional hazards models will also be fit to evaluate the final hazard ratio between the treatment arms, with exploratory modeling taking into account the potential influence of other factors (e.g., baseline disease burden, upfront vs. delayed nephrectomy). From these models, the hazard ratio for treatment assignment will be reported with a 70% confidence interval (to align with the overall alpha level of the primary log-rank test).

AEs: All Grade 3 or higher non-hematologic toxicities and all Grade 4-5 adverse events occurring during protocol therapy or within 100 days of treatment discontinuation, including crossover for patients who receive crossover combination therapy, will be analyzed. The rates of these events will be reported separately by treatment arm (including crossover as a “3rd” arm for this purpose), and both by individual AE and class of AE (e.g., hematologic). Given that some AEs may be rare, Fisher Exact tests will be used to test for statistical significance among any apparent differences by treatment arm.

Exploratory Analyses

Exploratory Aim 1.3.1: To characterize tRCC clinical behavior across all age groups.
We will list and summarize the frequency of site(s) of disease at presentation (including extent of lymph node involvement), site(s) of relapse, surgical practices on protocol therapy, and radiotherapy practices on protocol therapy. We will also summarize the overall response rate (ORR) submitted by the enrolling institution.

Exploratory Aim 1.3.2: To evaluate type of antitumor immune response and stability of T cell activation before and after treatment with immunotherapy or antiangiogenic therapy.

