11.3 Specific Examples for Expedited Reporting

11.3.1 SAEs Occurring More than 30 Days After Last Dose of Study Drug

Any Serious Adverse Event that occurs more than 30 days after the last administration of the investigational agent/intervention **and** has an attribution of a possible, probable, or definite relationship to the study therapy must be reported according to the CTEP-AERS reporting table in this protocol ([Section 11.8](#)).

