11.8 Reporting Table for Late Phase 2 and Phase 3 Studies

Expedited Reporting Requirements for Adverse Events that Occur on Studies under an IND/IDE within 30 Days** of the Last Administration of the Investigational Agent/Intervention¹

** Note expanded reporting timeframe of 100 days for AEs related to nivolumab (see Section 11.9.3)

FDA REPORTING REQUIREMENTS FOR SERIOUS ADVERSE EVENTS (21 CFR Part 312)

NOTE: Investigators **MUST** immediately report to the sponsor (NCI) **ANY** Serious Adverse Events, whether or not they are considered related to the investigational agent(s)/intervention (21 CFR 312.64)

An adverse event is considered serious if it results in **ANY** of the following outcomes:

- 1) Death.
- 2) A life-threatening adverse event.
- 3) Any AE that results in inpatient hospitalization or prolongation of existing hospitalization for \geq 24 hours. This does not include hospitalizations that are part of routine medical practice.
- 4) A persistent or significant incapacity or substantial disruption of the ability to conduct normal life functions.
- 5) A congenital anomaly/birth defect.
- 6) Important Medical Events (IME) that may not result in death, be life threatening, or require hospitalization may be considered serious when, based upon medical judgment, they may jeopardize the patient or subject and may require medical or surgical intervention to prevent one of the outcomes listed in this definition. (FDA, 21 CFR 312.32; ICH E2A and ICH E6.)

ALL SERIOUS adverse events that meet the above criteria **MUST** be immediately reported to the NCI via CTEP-AERS within the timeframes detailed in the table below.

Hospitalization	Grade 1 Timeframes	Grade 2 Timeframes	Grade 3 Timeframes	Grade 4 & 5 Timeframes
Resulting in Hospitalization \geq 24 hrs	7 Calendar Days			24-Hour Notification 5 Calendar Days
Not resulting in Hospitalization \geq 24 hrs	Not Required	7 Calendar Days		

NOTE: Protocol specific exceptions to expedited reporting of serious adverse events are found in the Specific Protocol Exceptions to Expedited Reporting (SPEER) portion of the CAEPR. Additional Special Situations as Exceptions to Expedited Reporting are listed below.

Expedited AE reporting timelines are defined as:

“24-Hour; 5 Calendar Days” - The AE must initially be reported via CTEP-AERS within 24 hours of learning of the AE, followed by a complete expedited report within 5 calendar days of the initial 24-hour notification.

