“7 Calendar Days” - A complete expedited report on the AE must be submitted within 7 calendar days of learning of the AE.

¹SAEs that occur more than 30 days after the last administration of investigational agent/intervention axitinib or more than 100 days after the last administration of investigational agent/intervention nivolumab, and have an attribution of possible, probable, or definite require reporting as follows:

Expedited 24-hour notification followed by complete report within 5 calendar days for:

- All Grade 4, and Grade 5 AEs

Expedited 7 calendar day reports for:

- Grade 2 adverse events resulting in hospitalization or prolongation of hospitalization
- Grade 3 adverse events

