11.10 Routine Reporting of Adverse Events

NOTE: The guidelines below are for routine reporting of study specific adverse events on the COG case report forms and do not affect the requirements for CTEP-AERS reporting.

Routine reporting is accomplished via the Adverse Event (AE) Case Report Form (CRF) within the study database. For this study, routine reporting will include all CTEP-AERS reportable events, all DLTs (see [Section 5.1](#)), and all Grade 3 and higher Adverse Events.

NOTE: For patients who receive nivolumab as part of this study, routine reporting of immune related AEs (IMAEs) must continue up to 100 days post last dose of nivolumab.

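### The AE comparison counts events of any cause to day 100, but Section 11 sets no matching collection rule for days 31 to 100

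*Combined protocol and SAP*

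**What the plan says.** Toxicity is the only secondary aim (Section 1.2). Section 9.3 says the AE endpoints will be formally compared at the final analysis. The set is every Grade 3 or higher non-hematologic event and "all Grade 4-5 adverse events occurring during protocol therapy or within 100 days of treatment discontinuation". No filter for attribution or immune origin is stated. Rates are given by arm, "including crossover as a “3rd” arm for this purpose", and "Fisher Exact tests will be used to test for statistical significance among any apparent differences by treatment arm".

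The collection rules are in Section 11. For routine CRF reporting, Section 11.10 lists expedited events, DLTs and all Grade 3 or higher AEs, without an end date. It then adds that "routine reporting of immune related AEs (IMAEs) must continue up to 100 days post last dose of nivolumab".

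For expedited reporting the base window in 11.8 is 30 days, with several different rules after that:
- 11.3.1 takes "Any Serious Adverse Event that occurs more than 30 days after the last administration of the investigational agent/intervention" if it is at least possibly related to study therapy.
- 11.3.3 and 11.7 put the same attribution condition on deaths after day 30.
- The note to the 11.8 table widens the window for nivolumab-related events: "Note expanded reporting timeframe of 100 days for AEs related to nivolumab (see Section 11.9.3".
- Footnote 1 to that table starts the attribution condition for nivolumab only "more than 100 days after the last administration of investigational agent/intervention nivolumab".
- 11.9.3 limits the 100-day extension to immune-related events.

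Section 11.6 sends every expedited event to the AE CRF as well.

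**The concern.** An analysis defined as all-cause to day 100 needs all-cause collection to day 100. Saying that immune-related reporting must continue to day 100 reads naturally as meaning that other reporting stops sooner. A site following Section 11 could therefore omit events that Section 9.3 counts.

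The late period matters for this drug. Section 5.3 warns that nivolumab events may appear several months after the last dose, and Section 6.2 states that the "geometric mean elimination half-life is 25 days". Section 11 does not define immune-related. ALT and AST rises, diarrhea, hypothyroidism, lipase and creatinine appear in the risk lists of both drugs, so the label is a judgement made at each site. If labels decide which late events reach the database, the between-arm test is no longer the all-cause comparison it is described as.

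**Working it through.** The plan gives no AE rate, AE power or AE sample size, so there is no stated figure to reproduce. The main check sets the rules side by side.

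| Section | Route | Covered after day 30 | Clock |
|---|---|---|---|
| 9.3 | analysis | all Grade 3+ non-hematologic and all Grade 4-5, any cause, to day 100 | treatment discontinuation |
| 11.10, list | routine | all Grade 3+; no end date given | none given |
| 11.10, note | routine | immune-related, to day 100 | last nivolumab dose |
| 11.3.1 | expedited | SAEs at least possibly related | last administration |
| 11.3.3, 11.7 | expedited | deaths at least possibly related | last dose |
| 11.8, note | expedited | nivolumab-related, to day 100 | last administration |
| 11.8, footnote 1 | expedited | attributed SAEs: after day 30 (axitinib), after day 100 (nivolumab) | last administration of that agent |
| 11.9.3 | expedited | immune-related, to day 100 | last nivolumab dose |

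**Test cases**
- *Unattributed death on day 45.* Counted by 9.3. Not reportable under 11.3.3 or 11.7, and outside the immune-related extensions. Only the undated list in 11.10 could bring it in.
- *Non-serious Grade 3 non-hematologic event on day 40, possibly related, not immune.* Counted by 9.3. Not an SAE, so 11.3.1 and footnote 1 do not apply, and not covered by the 11.10 note.
- *Serious event on day 40, possibly related.* Reportable under 11.3.1 and carried to the CRF by 11.6. Generally captured, subject to the SPEER exemptions from expedited reporting.

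The class without a stated rule is therefore unattributed Grade 3+ events and attributed non-immune events that are not serious. The exceptions are narrow: 11.3.2 and 11.7 take events causing persistent incapacity, and 11.7 takes important medical events, with no time limit or attribution condition.

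**Length of the gap.** If routine reporting of other events ended at the 30-day expedited limit (an assumption), 100 − 30 = 70 days are affected.

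**Clock.** In Section 4.3, axitinib runs Days 1-28. With nivolumab 480 mg on Day 1 only, the last axitinib dose can fall 28 − 1 = 27 days after the last nivolumab dose. A window of 100 days from nivolumab then ends 100 − 27 = 73 days after the last axitinib dose. With nivolumab on Days 1 and 15 the offset is 28 − 15 = 13 days.

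**Exposure.** Taking simple exponential decline at the 25-day half-life, the share of nivolumab left is 2^(−30/25) = 0.435 at day 30 and 2^(−100/25) = 0.0625 at day 100. At the longest axitinib half-life in Section 6.1, 5.2 hours, day 30 is 720/5.2 = 138 half-lives after the last dose.

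**Sensitivity (all rates and losses assumed).** With 28 patients at 1:1, about 14 per arm, one patient is 1/14 = 7.1 percentage points. The table takes true rates of 70% in Arm A and 40% in Arm C and a two-sided 0.05 Fisher test; the plan states neither level nor sidedness.

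| Affected patients missed, A / C | Observed rates | Difference | Power |
|---|---|---|---|
| none | 70% / 40% | 30 points | 21.6% |
| 10% / 10% | 63% / 36% | 27 points | 16.6% |
| 10% / 5% | 63% / 38% | 25 points | 14.0% |
| 5% / 10% | 66.5% / 36% | 30.5 points | 21.7% |

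With 10% missed in each arm, the patients lost are 14 × 0.07 = 0.98 in A and 14 × 0.04 = 0.56 in C. The difference can shrink or grow slightly, depending only on the assumed losses.

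**The case against.** The strongest reply is that no loss has been shown. The list in 11.10 already includes all Grade 3 or higher events and gives no stop date. The 30-day limit belongs to the expedited table, and 11.10 treats the two systems as separate. Appendix I says all AEs after baseline are entered in Rave. The CRF schedule that would settle the window is posted elsewhere and is not in the documents. Attributed SAEs stay reportable after day 30 and reach the CRF, so immune-related events are not the only late events collected. The 11.8 note is also wider than 11.9.3. All of this stands, and it makes undercounting a risk, not an established fact. It does not supply a sentence requiring every event in 9.3 to be collected to day 100. The statement in 11.8 that all SAEs are reported whether or not related sits under a title limited to 30 days.

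A reader might also infer that Arm A loses more late events, because sites there can attribute an event to axitinib, and that the combination would look safer than it is. The documents do not support this. Nivolumab is given in both arms, axitinib clears quickly, and an event possibly related to both drugs still counts as nivolumab-related. Serious events attributed to axitinib remain reportable. In Arm C, disease or later therapy are alternative causes. For ALT, AST and diarrhea, the SPEER exemption stops at Grade 2 for axitinib and Grade 3 for nivolumab, with the lower grade used for combinations. On the expedited route this favours fuller reporting in Arm A.

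**Conclusion.** The mismatch between analysis and collection is real and should be corrected. Section 9.3 counts all-cause events to day 100 from treatment discontinuation. Section 11 extends routine reporting explicitly only for immune-related events, from a different start date, and its expedited rules for days 31 to 100 conflict.

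The consequence is that the all-cause comparison may be incomplete after day 30 and may depend on site labels. The 70-day figure assumes that other routine reporting ends at day 30. The number of events affected, and the direction by arm, cannot be derived. The group size of 14 comes from the PFS target; Section 10.2.2.1 makes all treated patients evaluable for toxicity, so the actual groups may differ. If the CRF schedule already collects every Grade 3 or higher event to day 100, what remains is a clarification. If it does not, the comparison in 9.3 cannot be done as written. Sites cannot tell which applies from the protocol.

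**What to change.** In 11.10, require routine CRF reporting of every Grade 3 or higher AE, regardless of attribution, through 100 days after treatment discontinuation, for Arms A, C and crossover. Define treatment discontinuation as the last dose of any protocol agent and use that definition in 9.3 too. A clock from the last nivolumab dose would not do, since it can end up to 27 days before the 9.3 window. Flag events that follow subsequent anticancer therapy. Reconcile 11.3.1, 11.3.3, 11.7, 11.8 with its footnote 1, and 11.9.3 to one statement of what is reported on days 31 to 100.

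If collection is not extended, restrict the all-cause comparison in 9.3 to 30 days and describe later immune-related events separately, without a between-arm test.

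The cost is a wording change and modest extra CRF entry. No visit is added: the Month 3 follow-up in Section 7.2 falls near day 90, and events between then and day 100 can be recorded at the next contact. The drawback is that some recorded events will be due to subsequent therapy, which is why they need a flag.

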4.3.3 Treatment Details – Arm A: Axitinib + Nivolumab

Each cycle lasts 28 days (4 weeks). Absent disease progression or unacceptable toxicity, patients may continue on protocol therapy for up to 2 years duration or completion of 26 cycles, whichever comes first.

For patients who cross-over at disease progression on Arm C prior to Cycle 22, prior cycles received are included in total therapy calculations permitted on study.

Criteria to start each cycle: ANC \geq 1000/ μ L, platelet count \geq 75,000/ μ L without transfusion support. See [Section 5.0](#) for other requirements related to any ongoing toxicities.

Axitinib: PO

Days: 1 – 28

Dose: Age-based dosing as follows:

If \geq 18 years old: 5 mg/dose BID*

If $<$ 18 years old: 2.4 mg/m²/dose BID (maximum starting dose of 5 mg/dose)*. See [Appendix IV](#) for axitinib dosing nomogram and titrations.

NOTE: Dose is BID. For example, if age $<$ 18 years old administer 2.4 mg/m²/dose BID. The total daily dose is 4.8 mg/m²/day, divided BID (maximum starting dose is 5 mg/dose BID).

Axitinib should be taken by mouth twice daily approximately 12 hours apart. Axitinib may be taken with or without food. Tablets should be administered whole and intact with a glass of water or other liquid; do not crush or cut tablets. If a dose is missed or vomited, the patient/subject should not try to repeat or “catch up” the dose. The next dose should be given at the next regularly scheduled time point.

Axitinib will be distributed by the Division of Cancer Treatment and Diagnosis (DCTD), NCI. Do not use commercial supply.

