***NOTE:** Stopping or reducing the dose of axitinib is expected to cause a decrease in BP. The treating physician should monitor the patient for hypotension and adjust the number and dose of antihypertensive medication(s) accordingly.

5.2.5.4 Pediatrics (< 18 years of age):

Monitoring for children on axitinib will occur weekly during Cycle 1 (the period during which development of hypertension is most evident), and every other week thereafter. For patients who are dose escalated, weekly monitoring for the first cycle at the higher dose will also be required. Blood pressure will be measured with an appropriate sized cuff at rest. This can be monitored in the clinic or by alternative monitoring (home, pediatrician, alternative).

The algorithm in Figure 1 below provides guidelines for managing axitinib-related hypertension in pediatric patients.

Figure 1. Hypertension Management Algorithm for Pediatric Patients

Elevations in BP are based on systolic or diastolic pressures.

* Elevated blood pressure (BP) measurements should be repeated on the same day to confirm the elevation. Patients with elevated BP at any time should have BP measurements performed at least twice weekly until BP is within the ULN.

§ ULN (Upper Limit of Normal) is a BP equal to the 95th percentile from age, height, and gender-appropriate normal values (Appendix III).

* If BP > 25 mmHg above ULN for age (verified) or Grade 4 hypertension (HTN) at any time, hold axitinib. Axitinib should also be held for BP ≤ 25 mmHg above the ULN for > 14 days or 35 mmHg above baseline for > 14 days. Antihypertensive agents can be used to control hypertension as clinically indicated after axitinib is held.

NOTE: When axitinib is held and the patient is on antihypertensive treatment, the patient should be closely monitored for hypotension.

[^] Antihypertensive therapy should be prescribed as clinically indicated, including the use of multiple anti-hypertensive agents.

[°] Baseline BP is defined in Section 5.2.5.1.

Arm A of algorithm:

- If blood pressure (BP) \leq 95% for age, height, and gender, continue axitinib at the same dose.

Arm B of algorithm:

- If BP \leq 10 mm Hg above the ULN for age, height, and gender, continue axitinib at the same dose and recheck the BP within 72 hours.
 - If the BP is \leq ULN on recheck, continue axitinib at the same dose.

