A comprehensive simulation study was then performed, varying the following: the target sample size and maximum number of events required at the final analysis time point, the number and timing of interim analyses for futility, futility stopping strategies (conditional power under the alternative and current HR), and the true underlying hazard ratio (from $HR = 1.0$, the null hypothesis type I error scenario, to $HR = 0.40$, the target alternative hypothesis scenario). For all settings and strategies evaluated in simulations, accrual was assumed to be uniformly distributed as 24 patients per year (as reasoned above, acknowledging that slower than expected accrual will yield greater statistical power than reported here). PFS in the control arm was assumed to follow the piecewise exponential distribution shown in Figure 1B. With 100,000 replicates (simulated trials) used to assess each scenario, we arrived at the following trial design and set of operating characteristics.

The trial will enroll a target of 28 patients to observe 22 PFS events, which are required to achieve at least 80% power to detect a hazard ratio of $HR=0.40$ using a one-sided stratified log-rank test with $\alpha = 0.15$. If stratum-specific sample sizes allow, stratification of the test will include those factors used for stratification at the time of randomization (age and prior systemic therapy).

The trial will include one formal interim analyses for futility, conducted at 50% (11) of the required 22 PFS events. At this time, an observed hazard ratio greater than 1.00 (i.e., a

trend in the wrong direction) will result in early termination of the trial for futility. The simulated percentage change of early stopping for futility at the planned interim analysis (“early futility”), continuing to the final analysis but failing to reach statistical significance (“lack of efficacy”), and continuing to the final analysis and reaching statistical significance (“efficacy”) are tabled below for a range of true underlying hazard ratios. Also presented are the average simulated sample size (“Average N”) and average simulated time from reopening with Amendment 5A to final trial outcome (“Average Remaining Duration”) corresponding to each possible trial outcome. These numbers take into account the patients already enrolled, eligible, and anticipated to be evaluable for the primary endpoint.

True HR	Interim Analysis (50% Events)			Final Analysis (100% Events)			

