9.3 Methods of Analysis

Primary Endpoint Analyses

The primary endpoint, progression-free survival, is formally defined in [Section 9.4](#) below. Due to the small size of this trial and the need to preserve alpha-spending for the final analysis, there will be no formal interim analyses of PFS for early efficacy, though this trial will be periodically reviewed by the COG DSMC.

Prospective formal interim analyses for futility will be performed once 50% (11) of the 22 targeted PFS events have been observed. The trial will stop early for futility if, given the data observed to date, the observed hazard ratio for PFS is greater than 1.00, suggesting a trend toward worse outcomes for Arm A (nivolumab + axitinib) compared to Arm C (nivolumab alone).

The final PFS analysis will be performed based on the first quarterly data freeze where at least one of the following criteria are met: (1) a minimum of 2 years of follow-up has been obtained for each patient still “at risk” for a PFS event or (2) when at least 22 PFS events needed for a fully powered final analysis have been confirmed. At this time, a stratified, one-sided log-rank test (using the stratification factors at randomization, age and prior therapy, if stratum-specific sample sizes allow) will be performed to compare treatment arms with alpha = 0.15. A stratified Cox proportional hazards model will also be fit to evaluate the final hazard ratio between the treatment arms (stratification as numbers allow); this will be reported with a 70% confidence interval (to align with the overall alpha level of the primary log-rank test).

While post-progression outcomes on combination therapy among patients who receive crossover upon first progression on the nivolumab-only arm (Arm C) will not be counted toward the primary endpoint analyses, their post-progression experience, including time from first progression to second progression or death (second PFS) will be summarized descriptively.

Secondary Endpoint Analyses

Secondary endpoints OS and ORR (defined in [Section 9.4](#) below) as well as all Grade 3 non-hematologic adverse events and all Grade 4 and higher adverse events will be monitored for data cleanliness and routine reporting as well as formally compared at the time of the final analysis for the primary endpoint, as described below. For ORR and OS below, stratifications factors again may be collapsed and/or omitted depending on the final counts.

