All AEs that occur after baseline are collected in Medidata Rave using the Adverse Event form, which is available for entry at each treatment or reporting period and used to collect AEs that start during the period or persist from the previous reporting period. CRA will enter AEs that occur prior to the start of treatment on a baseline form that is not included in the Rave-CTEP-AERS integration. AEs that occur prior to enrollment must begin and end on the baseline Adverse Events form and should not be included on the standard Adverse Events form that is available at treatment unless there has been an increase in grade.

Prior to sending AEs through the rules evaluation process, site staff should verify the following on the Adverse Event form in Rave:

- The reporting period (course/cycle) is correct; and
- AEs are recorded and complete (no missing fields) and the form is query free.

The CRA reports AEs in Rave at the time the Investigator learns of the event. If the CRA modifies an AE, it must be re-submitted for rules evaluation.

Upon completion of AE entry in Medidata Rave, the CRA submits the AE for rules evaluation by completing the Expedited Reporting Evaluation form. Both NCI and protocol-specific reporting rules

evaluate the AEs submitted for expedited reporting. A report is initiated in CTEP-AERS using information entered in Medidata Rave for AEs that meet reporting requirements. The CRA completes the report by accessing CTEP-AERS via a direct link on the Medidata Rave Expedited Reporting Evaluation form.

In the rare occurrence that Internet connectivity is lost, a 24-hour notification is to be made to CTEP by telephone at [contact]. Once internet connectivity is restored, the 24-hour notification that was phoned in must be entered immediately into CTEP-AERS using the direct link from Medidata Rave.

Additional information about the CTEP-AERS integration is available on the CTSU website:

- Study specific documents: Protocols > Documents > Education and Promotion; and
- Expedited Safety Reporting Rules Evaluation user guide: Resources > CTSU Operations Information > User Guides & Help Topics.

NCI requirements for SAE reporting are available on the CTEP website:

- NCI Guidelines for Investigators: Adverse Event Reporting Requirements is available at https://ctep.cancer.gov/protocolDevelopment/electronic_applications/docs/aeguidelines.pdf

Data Quality Portal

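### The only planned between-arm AE test uses crude patient proportions over a window that lengthens with PFS; an exposure-aware comparison should be added beside it

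*Combined protocol and SAP*

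**What the plan says.** Section 1.2 has one secondary aim, which is to define the toxicities of the study arms. Section 9.3 says that Grade 3 non-hematologic and Grade 4 or higher AEs will be "formally compared at the time of the final analysis for the primary endpoint". Its AE paragraph defines the events as those "occurring during protocol therapy or within 100 days of treatment discontinuation, including crossover for patients who receive crossover combination therapy, will be analyzed". They are reported as rates by arm, with crossover as a third arm, and "Fisher Exact tests will be used to test for statistical significance among any apparent differences by treatment arm". The denominator of a rate is not defined, and no significance level or sidedness is given for these tests.

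Section 4.3.3 sets treatment length: absent progression or unacceptable toxicity, "patients may continue on protocol therapy for up to 2 years duration or completion of 26 cycles, whichever comes first". Section 4.5.3 has the same limit for Arm C and allows crossover at progression before Cycle 22. Section 9.3 plans no time-to-first-event, patient-time or common-window comparison of AEs. The one fixed safety window is the Cycle 1 DLT boundary in Section 9.5, which monitors each arm and does not compare arms.

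**The concern.** The length of time in which an AE can be counted depends on the primary outcome. If the combination delays progression as targeted, Arm A patients stay on treatment and under AE observation longer. More of them will then have at least one event, even if the risk in each month is the same in both arms. The planned table cannot separate a riskier regimen from longer treatment. The distortion works against the combination exactly when the combination works, and it falls on the trial's only stated secondary aim. Reporting crossover as a third arm does not adjust for exposure. It may also shorten Arm C's window at progression, because the text does not say which arm receives an event in the 100 days after nivolumab alone once the patient has crossed over.

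**Working it through.** **Inputs from the documents.** 28 patients randomised 1:1 (14 per arm), 22 PFS events, target HR 0.40, final analysis at 22 events or 2 years of follow-up (Sections 9.1-9.3); at most 26 cycles; 100-day tail. In Section 9.2 "accrual was assumed to be uniformly distributed as 24 patients per year", that is 2 per month. The table there is said to "take into account the patients already enrolled, eligible, and anticipated to be evaluable for the primary endpoint". Its interim rows imply how many those are: 24 - 9×2 = 6, 25 - 10×2 = 5, 26 - 10×2 = 6, so about 6.

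**Assumptions, not in the documents.** Exponential PFS with control median 5-6 months (the fitted piecewise model is in a figure not shown); the same AE hazard in both arms, independent of PFS; the tail kept in both arms; the interim futility look not modelled.

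**1. The plan's own figures.** Power with 22 events, one-sided alpha 0.15 and a stop at 11 events if the observed HR exceeds 1: the drift is √d(1-HR)/(1+HR), which at HR 0.4 is √11×0.6/1.4 = 1.42 at the interim and √22×0.6/1.4 = 2.01 at the end. With correlation √0.5 this gives 7.8% futility and 81.0% power, against 8% and 80% in the table. Simulated timing, with 6 earlier entries and 22 at 2 per month, puts the final cut at 15-17, 20-23 and 22-26 months after reopening for HR 1.0, 0.5 and 0.4. The table gives 17, 21 and 23. The assumed median range therefore fits the plan's timing.

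**2. Exposure, closed form.** With progression hazard λ and cap c, mean time on treatment is (1 - e^(-λc))/λ. For a control median of 5 months, λ = 0.1386 in Arm C and 0.4×0.1386 = 0.0555 in Arm A. With c = 24 months the means are 7.0 and 13.3 months, a ratio of 1.91.

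**3. Crude proportion, closed form.** With AE hazard a and tail τ = 100/30.44 = 3.29 months, P(at least one AE) = 1 - e^(-aτ)[λ/(λ+a)·(1 - e^(-(λ+a)c)) + e^(-(λ+a)c)]. At a = 0.05:
- Arm C: 1 - 0.8485×0.7378 = 37%
- Arm A: 1 - 0.8485×0.5636 = 52%

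The risk per month is identical. This version ignores the data cut, which shortens Arm A's follow-up more than Arm C's, so step 4 adds it.

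**4. With the data cut (simulation, 14 per arm, 5% per month).**

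| Control median | HR | Mean months on treatment, A vs C | Patients with an AE, A vs C | Gap |
|---|---|---|---|---|
| 5 | 0.4 | 11.4 vs 6.6 | 46% vs 36% | 10 points |
| 6 | 0.4 | 13.2 vs 7.8 | 51% vs 39% | 12 points |
| 5-6 | 0.5 | 9.7-11.4 vs 6.4-7.6 | 42-47% vs 35-38% | 7-9 points |
| 5-6 | 1.0 | equal | equal | 0 |

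Over medians of 4-8 months, the gap at HR 0.4-0.5 is 6-13 points.

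**5. Less favourable assumptions (medians 4-8 months, HR 0.4-0.5).**
- AEs front-loaded (10% per month for 3 months, then 2%): 3-6 points. Section 5.2.5.4 hints at this pattern for hypertension, calling Cycle 1 "the period during which development of hypertension is most evident".
- Constant 5%, with 3% per month toxicity stops in Arm A: 2-6 points.
- Front-loaded, with the same stops: 1-3 points.
- A single AE at 1% per month: 2-5 points.

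**6. The test.** At 5% per month Fisher at two-sided 5% rejects in about 3-5% of trials.

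**The case against.** The proportion of patients with a severe AE under a regimen as delivered, including longer treatment because the regimen works, is a legitimate measure, and nothing in the documents makes risk per month the required target. That stands, and it is why the crude table and its tests should stay.

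The gap is also small in patients: 10-12 points of 14 is about 1.5 patients (0.10×14 = 1.4; 0.12×14 = 1.7), and the smaller cases are less than one. The larger figures need HR 0.4, a constant hazard and no toxicity stops, although Section 5 contains many removal rules. Nor is 14 per arm the toxicity set: Section 10.2.2.1 counts all treated patients and accrual may reach 40. At 17-20 per arm, Fisher rejects in about 5-6% of trials. All of this limits the size of the point, not its direction.

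Three stronger readings are tempting, and the documents do not support them:
- **Fisher will produce false safety signals.** At one-sided 0.15 it would reject in 27-30% of trials (40% of Arm C with the AE, 24-month cap, both tails kept). Section 9.3 sets that level for PFS and OS, not for AEs.
- **The gap is 16-22 points because Arm C's window closes at crossover while Arm A keeps its tail.** The text leaves this open. It does not state that Arm C keeps its tail either, so tails in both arms is an assumption here and not the plan.
- **Time to first event removes the bias.** It does so only if AEs and progression are independent. With a shared frailty (variance 0.5-1), first-event rates censored at progression still give an A:C ratio of about 1.1-1.2 at equal risk.

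**Conclusion.** The point holds as a cheap improvement to Section 9.3. The only formal AE comparison is on patient proportions over a window that grows with PFS, and nothing else in the plan compares Arm A with Arm C on equal exposure. Under the stated assumptions, the excess in Arm A that reflects longer observation alone is about 10-12 points at HR 0.4 and 7-9 at HR 0.5. It is about 1-6 points if AEs come early, are rare, or lead to more stops in Arm A, and it vanishes at HR 1.0. The control median, the AE hazards and the tail after crossover are all assumed. The harm is mainly descriptive: readers of a positive trial could take longer treatment for a more toxic regimen. It does not show that the crude analysis is invalid or that a spurious significant result is likely, and the primary PFS analysis is not affected.

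**What to change.** In Section 9.3, define the rate as patients with an event over patients treated, and keep these proportions and the Fisher tests as the as-delivered description. For Arm A versus Arm C, add:

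1. Patient-months at risk by arm.
2. Time to first event for the main AE classes, with cumulative incidence at a common early time such as 6 cycles and death as a competing event. End time at risk by the same rule in both arms: the end of the randomised regimen, which for Arm C patients who cross over is the first axitinib dose.
3. The crossover period and the 100-day tail reported separately, each with its own patient-months, plus a sensitivity run that adds the tail where it is observed.
4. A statement of which arm receives events after nivolumab alone once a patient has crossed over.

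Do not apply the crossover cut to the crude proportions while Arm A keeps its tail; under the same assumptions that widens the spurious gap to 16-22 points.

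**Cost.** A wording change and a little more analysis. The delivery maps in Section 4 record dates given, and the AE form in Appendix I is "used to collect AEs that start during the period or persist from the previous reporting period", so timing may be known only to the nearest cycle. Censoring at progression may be informative, so the added result is less biased, not unbiased. Delayed nivolumab events can fall in the crossover period and need a footnote. Sparse individual AEs should be given as counts and patient-months without a time-to-event analysis.
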